### 6.4 CONCOMITANT THERAPY

For this protocol, a prescription medication is defined as a medication that can be prescribed only by a properly authorized/licensed clinician. Medications to be reported in the Case Report Form (CRF) are concomitant prescription medications, over-the-counter medications and supplements. Medication information will be collected at each neurocognitive assessment visit. A list of medications will be extracted from the most recent available medical records and confirmed in person with the patient. This will be performed by the study coordinator.

---

#### 6.4.1 RESCUE MEDICINE

The study site will not supply rescue medication that will be obtained locally.

The following rescue medications / treatments may be used in the setting of hemorrhagic adverse events at the discretion of the treating physician.

**Apixaban:** Discontinue therapy with active pathological hemorrhage and promptly evaluate for bleeding source.

A specific antidote for Apixaban is not available, and there is no established way to reverse bleeding in patients taking Apixaban. The pharmacodynamic effect of Apixaban can be expected to persist for at least 24 hours after the last dose, i.e., for about two drug half-lives. Use of procoagulant reversal agents, such as prothrombin complex concentrate (PCC), activated prothrombin complex concentrate or recombinant factor VIIa, may be considered but has not been evaluated in clinical studies. When PCCs are used, monitoring for the anticoagulation effect of apixaban using a clotting test (PT, INR, or aPTT) or anti-factor Xa (FXa) activity is not useful and is not recommended. A preclinical study evaluated the impact of different clotting factors in reversing actions of apixaban. A high concentration of apixaban (200 ng/mL) was added to blood from healthy donors *in vitro* and blood-clotting response was evaluated when prothrombin complex concentrates (PCCs; product not specified), activated prothrombin complex concentrates (aPCCs), and recombinant factor VII (rFVIIa) were added. PCC and aPCC seemed to be more efficient in restoring generation of thrombin, while rFVIIa was the quickest to produce a compact blood clot and most effective in studies with blood circulating through a damaged blood vessel. Activated oral charcoal reduces absorption of apixaban, thereby lowering apixaban plasma concentration. The use of activated oral charcoal

may be considered if ingestion occurred within 2 to 6 hours of presentation. Hemodialysis does not appear to have a substantial impact on apixaban exposure. Protamine sulfate and vitamin K are not expected to affect the anticoagulant activity of apixaban. There is no experience with antifibrinolytic agents (tranexamic acid, aminocaproic acid) in individuals receiving apixaban. There is no experience with systemic hemostatics (desmopressin and aprotinin) in individuals receiving apixaban, and they are not expected to be effective as a reversal agent.

*Warfarin:* If bleeding occurs, check INR and discontinue use. Depending on the severity of the bleeding intravenous fresh frozen plasma and oral or intravenous Vitamin K can be used to reverse the anticoagulant effect of warfarin.

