## 7 STUDY INTERVENTION DISCONTINUATION AND PARTICIPANT DISCONTINUATION/WITHDRAWAL

### 7.1 DISCONTINUATION OF STUDY INTERVENTION

Discontinuation from study intervention (anticoagulant use) does not mean discontinuation from the study, and remaining study procedures should be completed as indicated by the study protocol. If a clinically significant finding is identified (including, but not limited to changes from baseline) after enrollment, the investigator or qualified designee will determine if any change in participant management is needed. Any new clinically relevant finding will be reported as an adverse event (AE). Events that may trigger include:

1. Major bleeding event. The anticoagulant will be discontinued and future management of anticoagulant will be decided by the treating physician. The patient will not be re-challenged with anticoagulant as part of the study protocol.
2. Ischemic Stroke / TIA. Management of anticoagulant in the first month following an ischemic stroke / TIA will be determined by the treating physician. Following this, a decision regarding whether to continue study intervention will be made in consultation with the treating physician and the patient. Whether the anticoagulant was being used in a therapeutic fashion at the time of event will be part of this discussion.
3. Hemorrhagic stroke. The study intervention will be discontinued and future anticoagulation decision will be made by the treating physician.
4. Participants will be strongly encouraged by the study staff to remain on treatment assigned through randomization and to comply with the study protocol and follow-up. However, participants or their physician may voluntarily discontinue study intervention or change OAC treatment at any time. Study staff will make every effort to discourage this.

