### *Clinically Relevant nonmajor Bleed*

A clinically relevant minor bleed is an acute or subacute clinically overt bleed that does not meet the criteria for a major bleed but prompts a clinical response, in that it leads to at least one of the following:

- A hospital admission for bleeding, or
- A physician guided medical or surgical treatment for bleeding, or
- A change in antithrombotic therapy (including interruption or discontinuation of study drug).

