### *Minor Bleeding*

All acute clinically overt bleeding events not meeting the criteria for either major bleeding or clinically relevant nonmajor bleeding will be classified as minor bleeding.

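### Sections 6.4.1 and 7.1 word the stopping of anticoagulant after a bleed differently by arm, and because any stop counts towards clinically relevant nonmajor bleeding, by-arm splits of that grade against minor bleeding are open to differential classification

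*Combined protocol and SAP*

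**What the plan says.** Three places in the combined protocol and SAP speak to stopping anticoagulant because of bleeding.

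- Section 6.4.1, warfarin: "If bleeding occurs, check INR and discontinue use". The sentence that follows makes plasma and vitamin K depend on severity; the stop itself carries no such qualifier.
- Section 6.4.1, apixaban: "Discontinue therapy with active pathological hemorrhage and promptly evaluate for bleeding source".
- Section 7.1, both arms: "Major bleeding event. The anticoagulant will be discontinued and future management of anticoagulant will be decided by the treating physician". Hemorrhagic stroke is listed separately, also for both arms.

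The lead-in to 6.4.1 applies to both drugs and says that the listed measures "may be used in the setting of hemorrhagic adverse events at the discretion of the treating physician".

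Section 8.2 then grades bleeds. An overt bleed that is not major is clinically relevant nonmajor (CRNM) if it meets any one of three criteria: a hospital admission, "A physician guided medical or surgical treatment for bleeding, or" the third, "A change in antithrombotic therapy (including interruption or discontinuation of study drug". Minor bleeding is the residual class: bleeds "not meeting the criteria for either major bleeding or clinically relevant nonmajor bleeding will be classified as minor bleeding".

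Section 6.3 leaves participants, the principal investigator and the coordinator unblinded, and blinds only the personnel handling MRI and cognitive testing. Section 10.1.5 has the DSMB review safety data by arm at least twice a year.

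**The concern.** One CRNM criterion is an action by the clinician, namely interrupting or stopping the drug. The written guidance on when to take that action is broader for warfarin than for apixaban, and the people taking it know the arm. If clinicians follow the guidance even in part, two bleeds of the same severity can be graded differently: minor on apixaban, CRNM on warfarin. A table of bleeds by grade and arm could then show an excess of CRNM bleeding on warfarin that reflects the wording and not the drugs.

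There is a second route, into the efficacy data. Section 7.1 says that stopping the intervention does not by itself end study participation, but a participant who changes oral anticoagulant is withdrawn and censored at that time. If one arm's wording prompts more stops, and some of those become a change of drug, follow-up for cognition and MRI is lost unevenly between arms.

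**Working it through.** **No plan figure to reproduce.** The documents give no rate of nonmajor bleeding, no rate of stopping after a bleed, and no planned analysis of bleeding grades. Section 2.3.1 reports that 1.7% (apixaban) and 2.5% (warfarin) of patients in an earlier trial stopped for bleeding-related reactions. Those are shares of all patients, not of patients with a nonmajor bleed, so they do not supply the quantity needed here.

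**Step 1: the texts side by side.** Take an overt bleed that is not major, needs no admission and gets no physician-guided treatment.

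| | Warfarin | Apixaban |
|---|---|---|
| 6.4.1 wording met? | Yes; any bleeding | Only if it is active pathological hemorrhage, a term the documents do not define |
| 7.1 major-bleed trigger met? | No | No |
| Grade if drug is stopped | CRNM | CRNM |
| Grade if drug is not stopped | Minor | Minor |

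The grading rule is the same in both arms. What differs is how readily the guidance prompts a stop. Within the warfarin arm, 6.4.1 and 7.1 also name different thresholds.

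**Step 2: which grades can move.** The major-bleed definition in 8.2 rests on fatality, critical site, hemoglobin fall or transfusion. None depends on stopping drug. The total of overt bleeds does not depend on it either. Only the boundary between CRNM and minor can shift.

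**Step 3: an illustration of size.** All inputs except arm size are assumptions.

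- b = risk of an overt nonmajor bleed, equal in both arms: 10% to 30%.
- c = share of those that are CRNM through admission or treatment anyway: 30% to 50%.
- s = probability of a stop among the rest, varied by arm.
- Arm size 140, from section 9.2.

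CRNM risk = b × (c + (1 − c) × s). In the ratio between arms b cancels, so the ratio depends only on c and s.

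For stopping of 20% on apixaban and 50% on warfarin:

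- c = 30%: (0.30 + 0.70 × 0.50) / (0.30 + 0.70 × 0.20) = 0.65 / 0.44 = 1.48.
- c = 50%: (0.50 + 0.50 × 0.50) / (0.50 + 0.50 × 0.20) = 0.75 / 0.60 = 1.25.

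| Stopping, apixaban vs warfarin | Warfarin:apixaban CRNM ratio |
|---|---|
| 20% vs 20% | 1.00 |
| 20% vs 50% | 1.25 to 1.48 |
| 20% vs 100% | 1.67 to 2.27 |
| 0% vs 100% | 2.00 to 3.33 |

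In counts, with b = 20%, c = 50% and stopping of 20% vs 50%, the expected CRNM bleeds are 140 × 0.12 = 16.8 on apixaban and 140 × 0.15 = 21.0 on warfarin. A two-sided 0.05 test of those proportions would be significant with probability about 0.11 although true bleeding is equal. No such test is planned; the figure only shows scale.

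**The case against.** The strongest reply is that 6.4.1 is discretionary. Its lead-in covers both drugs, and warfarin is managed by the treating physician or anticoagulation clinic in any case (section 6.2). Section 7.1 gives both arms the same bleeding triggers and has staff discourage voluntary discontinuation. A reader might infer that sites are ordered to stop warfarin for any bleed, so that a minor bleed can never be recorded in that arm. The documents do not support this. Besides the discretion, adverse events are picked up by interview at the 1- and 2-year visits and by record review (sections 8.1 and 8.2). A brief bleed that resolved at home and was reported later led to no stop, and is minor in either arm.

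Second, clinical bleeding is not an endpoint in section 3 or 9.1, and the Cox models in 9.4.1 cover MCI/dementia, infarction and microbleeds. A reader might take bleeding as the main safety outcome and its comparison as already biased. No passage gives it that status, and no comparison of grades is prespecified.

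Third, some protection exists. A DSMB physician grades the intensity of each adverse event by its effect on daily activities (8.3.3.1), which does not depend on stopping drug, and a CRF collects the reason for discontinuation (7.1).

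All of this stands, and it narrows the point. It does not remove it. Discretionary guidance that differs by arm, used by clinicians who know the arm, is still a route to differential grading, and no blinded classification of bleeds is described. The bleeding grades are the adverse events that 8.2 chooses to define, and safety data will be viewed by arm. A CRF on discontinuation does not say which CRNM criterion a bleed met.

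**Conclusion.** The point holds in a limited form. The stopping wording in 6.4.1 and 7.1 differs by arm and needs reconciling. While it differs, any by-arm split of CRNM against minor bleeding is open to differential classification against warfarin. Major bleeding and total overt bleeding are not affected. Arm-specific withdrawal and censoring follows only where a stop becomes a change of anticoagulant.

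The size cannot be derived from the documents. It is nil if stopping is equal in the two arms. With assumed stopping of 20% against 50%, and 30% to 50% of nonmajor bleeds qualifying as CRNM in any case, the apparent warfarin:apixaban ratio is about 1.25 to 1.48. The ratios of 2.00 to 3.33 come from reading the text literally, with every such bleed stopping warfarin and none stopping apixaban. Discretionary wording does not support that reading, and those ratios should not be quoted as the expected effect.

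The change is worth making because it is cheap and removes an avoidable ambiguity from the safety tables. It does not threaten a prespecified analysis of bleeding, since there is none.

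**What to change.** - Reconcile the warfarin and apixaban text in 6.4.1 with the bleeding item in 7.1, so that the same wording on stopping for bleeding applies to both arms. What that wording should be is a clinical decision for the sponsor.
- Add a CRF field recording which 8.2 criterion made each bleed CRNM: admission, treatment, or change in antithrombotic therapy.
- In by-arm safety reports, show CRNM bleeding with and without the drug-change criterion, alongside major bleeding and all overt bleeding.

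The CRNM definition in 8.2 is the same for both arms and need not be rewritten. The cost is a wording amendment, one CRF field and one extra table row.

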## 7 STUDY INTERVENTION DISCONTINUATION AND PARTICIPANT DISCONTINUATION/WITHDRAWAL

### 7.1 DISCONTINUATION OF STUDY INTERVENTION

Discontinuation from study intervention (anticoagulant use) does not mean discontinuation from the study, and remaining study procedures should be completed as indicated by the study protocol. If a clinically significant finding is identified (including, but not limited to changes from baseline) after enrollment, the investigator or qualified designee will determine if any change in participant management is needed. Any new clinically relevant finding will be reported as an adverse event (AE). Events that may trigger include:

1. Major bleeding event. The anticoagulant will be discontinued and future management of anticoagulant will be decided by the treating physician. The patient will not be re-challenged with anticoagulant as part of the study protocol.
2. Ischemic Stroke / TIA. Management of anticoagulant in the first month following an ischemic stroke / TIA will be determined by the treating physician. Following this, a decision regarding whether to continue study intervention will be made in consultation with the treating physician and the patient. Whether the anticoagulant was being used in a therapeutic fashion at the time of event will be part of this discussion.
3. Hemorrhagic stroke. The study intervention will be discontinued and future anticoagulation decision will be made by the treating physician.
4. Participants will be strongly encouraged by the study staff to remain on treatment assigned through randomization and to comply with the study protocol and follow-up. However, participants or their physician may voluntarily discontinue study intervention or change OAC treatment at any time. Study staff will make every effort to discourage this.

Participants who change OAC treatment during follow-up will be withdrawn from the study. A CRF will collect details of the reason for discontinuation of study intervention. Endpoints will be assessed at the time of withdrawal from the study including MRI and cognitive function. The MRI of the head and / or cognitive assessment will be performed at the time of withdrawal from the study if it is greater than 6 months since their last assessment of MRI and / or cognitive function. If a patient withdraws within 6 months of the last assessment, repeat testing will not be performed and the last assessment will be used for the analysis. Participants who withdraw from the study will be followed for 30 days after withdrawal for adverse events. A primary intention to treat analysis will be performed at the end of the study. Participants who withdraw or change OAC treatment will be censored at the time of withdrawal.

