To assess the development of mild cognitive impairment or dementia	
Clinical dementia rating scale
 
Dementia Subjects with a CDR 1 will be classified as demented if they meet DSM-V criteria for ‘major neurocognitive disorder’ as follows:
 
 
1. Evidence of significant cognitive decline from a previous level of performance in one or more cognitive domains based on:               
 
a. Concern of the individual, a knowledgeable informant, or the clinician that there has been a significant decline in cognitive function; and
 
b. A substantial impairment in cognitive performance, preferably documented by standardized neuropsychological testing.
 
 
 
2. The cognitive deficits interfere with independence in everyday activities.
 
3. The cognitive deficits do not occur exclusively in the context of delirium and are not better explained by another mental disorder.
 
 
For subjects with CDR 0.5, a committee of the examining
	The development of dementia or mild cognitive impairment are important end points with clinical relevance to the patient.

OBJECTIVES	ENDPOINTS	JUSTIFICATION FOR ENDPOINTS
	
neuropsychologist and physician will critically examine the available tests to determine whether the DSM-V criteria for dementia or MCI are met.
 
Mild cognitive impairment                      The criteria for diagnosis of MCI are: cognitive concern expressed by a physician, informant, participant or nurse; cognitive impairment in 1 or more domains; normal functional activities and not demented. Subjects with MCI can have a CDR of 0 or 0.5; however, the final diagnosis of MCI will not be based exclusively on the CDR but rather on all available data. A committee of the examining neuropsychologist and physician will critically examine the available tests to determine whether the criteria for MCI are met.
	
Tertiary end points		
MRI detected new cerebral ischemic lesions and cerebral microbleeds (CMBs)	Brain MRI will be performed at baseline and 2 years to assess the presence of new cerebral ischemic lesions on DTI imaging and new cerebral microbleeds on SWAN sequences.	The presence of cerebral infarcts, even clinically silent ones, have been associated with higher future risk of dementia. Similarly, CMBs are associated with dementia and future risk for intracerebral hemorrhage.

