## 9.2 SAMPLE SIZE DETERMINATION

Sample size calculation is based on the primary endpoint, the rate of decline in the global cognitive function score. The sample size calculations are based on data from the Mayo Clinic Study of Aging which has enrolled community dwelling individuals to perform the same battery of neurocognitive tests proposed in this study. We investigated the rate of decline in the global cognitive function score in (1) patients with and without AF and (2) in AF patients on warfarin vs. not on warfarin. The Mayo Clinic Study of Aging (MCSA) has identified a significant decline in the individual and global cognitive function scores in patients with AF compared to those without AF. In addition, the rate of decline was similar in AF patients treated with warfarin and those not treated with warfarin. The observed rate of decline in global cognitive score in AF patients on warfarin was -0.12 / year (SD 0.16). A reduction in the rate of decline in the global cognition function score of 0.05/year with Apixaban compared to Warfarin was considered clinically relevant. We used R to calculate power as a single sided test of superiority of Apixaban over Warfarin. A sample size of 140 in each arm is required to achieve >80% power to detect

the difference stated assuming an alpha error of 0.05. Assuming a screen failure rate of 20%, a total of 175 will be accrued in each arm.

Enrollment will be age and gender stratified with goal of enrolling >50% patients over the age of 70 years in whom the risk of cognitive decline is greater. Recruitment of the required number of subjects will be feasible given the high volume of AF patients in the local community and those seeking care for AF at the Mayo Clinic. For example, 5000 individuals developed incident (new onset) AF in Olmsted county alone after the year 2000. The rate of prevalent AF is higher in this population. The other 7 counties from which participants will be recruited have similar population demographics and prevalence of AF. We anticipate that we will be able to recruit the required number of subjects in the first year of the study.

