### 9.4 STATISTICAL ANALYSES

#### 9.4.1 GENERAL APPROACH

Continuous and categorical variables will be summarized as mean (standard deviation, SD) and number (%) respectively. Differences between the two treatment arms at baseline will be examined using t-tests for continuous variables and chi-square tests for categorical variables.

The baseline variables include age, sex, education, cardiovascular risk factors (hypertension, diabetes mellitus, hyperlipidemia), past medical history (including stroke, TIA, heart failure, peripheral arterial disease, MI, coronary artery disease, liver disease, renal disease, malignancy), duration of AF, pattern of AF (paroxysmal, persistent), prior h/o anticoagulation (duration and type of drug used), prior treatment of AF (antiarrhythmic drug, ablation procedure), and current medications. This data will be reviewed and updated at each visit. The INR values during the study will be collected for patients on warfarin and the time in therapeutic range calculated using the Rosendaal method of interpolation.

Longitudinal changes in each cognitive domain (language, attention, memory, visual spatial and global) will be analyzed using multiple adjusted linear mixed effects models comparing Apixaban vs warfarin. These models will be adjusted for baseline variables that differ between the groups. These results will be presented as beta estimates for baseline differences in cognitive function score by treatment status, change with time and the effect of treatment on the change in scores over time.

For the secondary end point of dementia/MCI, the mid-point between the most recent visit with a cognitively normal diagnosis and the first visit with a diagnosis of MCI or dementia will be considered the date of onset. Participants who are lost to follow-up or die during follow-up will be censored at the

date of last follow-up. Cox proportional hazards model will be used to assess the secondary end points of MCI/dementia, cerebral infarction and cerebral microbleeds. Adjustment for baseline factors noted above will be performed in the multivariable model.

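### Section 7.1 lets a baseline MRI stand as the outcome scan for early withdrawals, and conflicts with the plan's censoring and withdrawal-scan instructions

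*Combined protocol and SAP*

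**What the plan says.** Four places in the protocol bear on a patient who leaves early.

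- **Schedule.** Section 3: "Brain MRI will be performed at baseline and 2 years to assess the presence of new cerebral ischemic lesions on DTI imaging". Sections 4.1 and 8.1 give the same two time points. Cognition is tested at baseline, 1 year and 2 years.
- **Withdrawal rule.** Section 7.1 asks for an MRI, a cognitive assessment or both at withdrawal if more than 6 months have passed since the last one. Within 6 months, "repeat testing will not be performed and the last assessment will be used for the analysis". The section then ends by censoring patients at withdrawal or at a change of anticoagulant.
- **Imaging procedure.** Section 8.1, under MR imaging of the brain, says an MRI will be attempted before any withdrawal that precedes the end of follow-up. It sets no 6-month condition.
- **Analysis.** Section 9.4.1: "Cox proportional hazards model will be used to assess the secondary end points of MCI/dementia, cerebral infarction and cerebral microbleeds". Its rule for dating onset at a midpoint between visits is written for MCI/dementia; no dating rule is given for MRI lesions.

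No section says how a patient whose only scan is the baseline one enters the MRI analysis.

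**The concern.** The MRI endpoint is a *new* lesion, so it needs two scans. Read literally, Section 7.1 supplies the second scan for an early withdrawal by reusing the first. The comparison is then of a scan with itself, and the answer is always no new lesion.

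This matters for the treatment comparison because early withdrawal may differ by arm. The trial is open-label, and Section 7.1 withdraws from the study anyone who changes anticoagulant. Scoring such patients as lesion-free would flatter whichever arm loses more of them.

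A second difficulty is the 6-month clock. Section 7.1 refers to MRI and/or cognitive function without saying whether each has its own clock. If a recent cognitive test is enough, a patient who withdraws between about months 12 and 18, soon after the year-1 test, could also go unscanned.

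**Working it through.** **The plan's own figure.** The documents give no lesion rate, withdrawal rate or power for MRI. The only sample-size figure is for cognition (Section 9.2): difference 0.05/year, SD 0.16, one-sided alpha 0.05, 140 per arm. The standard error is 0.16 × √(2/140) = 0.0191, so z = 0.05/0.0191 = 2.61, and power = Φ(2.61 − 1.645) = 83%. This agrees with the stated power above 80%. The accrual figure also reproduces: 140/0.80 = 175. Neither depends on the MRI rule.

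**Who is exposed.** If MRI has its own clock, only withdrawals in months 0–6 have no second scan; later ones are to be scanned. If a cognitive test also resets the clock, withdrawals in about months 12–18 are added, so the exposed period grows from 6 to about 12 of the 24 months.

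**Reading A: the baseline scan is carried forward as the 2-year outcome.** Let p be the true 2-year lesion risk and w the share withdrawing unscanned. Both are assumptions, and withdrawal is taken as unrelated to lesion risk. Observed risk = p × (1 − w).

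| p | w = 5% | w = 10% | w = 15% |
|---|---|---|---|
| 10% | 9.5% | 9.0% | 8.5% |
| 20% | 19.0% | 18.0% | 17.0% |
| 30% | 28.5% | 27.0% | 25.5% |

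With no true effect, p cancels and the apixaban/warfarin risk ratio is (1 − w_apixaban)/(1 − w_warfarin):

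- 5% vs 5%: 1.00
- 5% vs 10%: 0.95/0.90 = 1.06
- 5% vs 15%: 0.95/0.85 = 1.12
- 5% vs 20%: 0.95/0.80 = 1.19
- 15% vs 5% (reversed): 0.85/0.95 = 0.89, now favouring apixaban

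In patients, with p = 20% and 140 per arm, 28 lesion-positive patients are expected in each arm. At 5% vs 15% the count becomes 28 × 0.95 = 26.6 against 28 × 0.85 = 23.8.

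**Reading B: the patient is censored at withdrawal.** A Cox simulation used 100,000 patients per arm, true hazard ratio 1, p = 20%, early withdrawals without a scan, and a further 10% per arm withdrawing later with a scan. Hazard ratios, apixaban to warfarin, were:

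| Early withdrawal (apixaban / warfarin) | Carried to 2 years | Censored, lesion dated at scan | Censored, lesion dated halfway to scan |
|---|---|---|---|
| 10% / 10% | 1.02 | 1.00 | 0.99 |
| 5% / 15% | 1.13 | 0.99 | 1.00 |
| 5% / 20% | 1.23 | 0.98 | 1.01 |

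Each cell is one run. The first row under carry-forward should be exactly 1 and came out at 1.02, so departures of 2% or so should not be interpreted. A closed-form check that ignores the later withdrawals gives ln(0.81)/ln(0.83) = 1.13 and ln(0.81)/ln(0.84) = 1.21 for the last two carry-forward rows. Censoring stays near 1 because early withdrawals have left the risk set before most lesions are recorded.

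**The case against.** The strongest defence is that Section 7.1 should be read whole. It ends by censoring withdrawals, and Section 9.4.1 analyses lesions with a Cox model, so an early withdrawal leaves the risk set and is not counted as lesion-free at 2 years. A fixed 2-year proportion with withdrawals kept in the denominator is not specified anywhere. Section 8.1 goes further and asks for an attempted MRI before any early withdrawal. This stands as a limit on the claim: the biased analysis is one permitted reading, not the plan's settled method. It does not remove the problem. The instruction to use the last assessment and the instruction to censor sit side by side with no order of precedence, and Section 8.1 contradicts the 6-month exemption without overriding it. Censoring is also harmless only if withdrawal is unrelated to lesion risk.

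Two further inferences are tempting and are not supported:

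- *That the rule carries cognitive scores forward to year 2 and so biases the primary endpoint.* Section 7.1 says the last assessment is used; it does not move it to a later date. Section 9.4.1 specifies linear mixed models for change over time, and Section 9.1 censors from the primary analysis patients who stop attending in person. Using the scores observed so far is ordinary mixed-model practice.
- *That every bleed or stroke forces a patient out of the study.* Section 7.1 opens by separating stopping the drug from leaving the study. Mandatory withdrawal follows a change of anticoagulant; withdrawal for an adverse event is at the investigator's discretion under Section 7.2.

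**Conclusion.** The point holds as a conflict between instructions, one reading of which biases the MRI endpoints. A reader might infer that early withdrawals are scored lesion-free by construction. That is true only if the baseline scan is used as the outcome, and the censoring sentence and the Cox model point the other way.

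Bias in the treatment comparison needs two conditions: the baseline scan carried to 2 years, and early withdrawal that differs by arm. Under both, with no true effect, the spurious risk ratio is 1.06 to 1.19 for assumed withdrawal of 5% on apixaban against 10% to 20% on warfarin, and about 1.12 at 5% against 15%. The direction follows the arm with more early withdrawals. With equal withdrawal the ratio is unchanged, although both lesion risks are understated. Under censoring the simulated hazard ratio is 0.98 to 1.01 unless withdrawal is informative.

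The damage is confined to the MRI endpoints, which the synopsis and Section 9.1 call secondary and Section 3 calls tertiary. The primary endpoint and the sample size are untouched. The change is worth making because it is cheap and settles, before any data are seen, a choice that can move the result.

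**What to change.** 1. Reconcile Sections 7.1, 8.1 and 9.4.1 so that one rule says when a withdrawal MRI is sought and how the patient then enters the analysis.
2. State that the 6-month clock runs separately for MRI and for cognition.
3. Replace the last-assessment sentence in Section 7.1 with:

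> No value is carried forward. Each cognitive score enters the mixed model at its actual date. A baseline scan is never used as a follow-up outcome. Patients with no MRI after baseline are treated as missing for the MRI endpoints, with multiple imputation as a sensitivity analysis.

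4. Align the censoring sentence in Section 7.1 with this wording, and say how new MRI lesions are dated in the Cox model.
5. Report early withdrawal by arm, with reasons, so that readers can judge whether it was differential or informative.

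The cost is a few sentences of protocol text, one sensitivity analysis and one table. The downside is a slightly smaller observed MRI sample. The sentence on cognitive dates only makes explicit how a mixed model would ordinarily use the scores.
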